3.8 DOSING DELAYS AND MODIFICATIONS

Subjects should be followed closely for AEs or laboratory abnormalities that might indicate acalabrutinib- or pembrolizumab-related toxicity. If a subject experiences a treatment-related DLT or other intolerable AE during the course of therapy, then acalabrutinib, pembrolizumab, or both drugs should be held, as necessary, until the AE resolves or stabilizes to an acceptable degree. In cases where pembrolizumab is held, pembrolizumab should be restarted in agreement with its original dosing schedule (every 3 weeks). As appropriate, certain laboratory abnormalities may warrant more frequent monitoring (eg, once per week) until abnormalities have recovered to Grade ≤ 1 . Dose reductions for acalabrutinib are provided in [Table 3-2](#). If acalabrutinib is reduced for apparent treatment-related toxicity, the dose need not be re-escalated, even if there is minimal or no toxicity with the reduced dose. However, if the subject tolerates a reduced dose of acalabrutinib for ≥ 4 weeks then the dose may be increased to the next higher dose level, at the discretion of the investigator. Such re-escalation may be particularly warranted if further evaluation reveals that the AE that led to the dose reduction was not treatment-related. However, the maximum dose of acalabrutinib is 100 mg BID for this protocol.

For treatment-emergent hepatotoxicity in the combination arm or for subjects who cross over to receive combination therapy: Important guidelines for treatment-emergent hepatotoxicity are provided in [Section 3.8.2](#) for pembrolizumab. In the combination arm or for subjects who cross over to receive combination therapy, treatment with acalabrutinib should be withheld for Grade 3 or 4 hepatitis. For Grade 4 events, acalabrutinib may be restarted only after discussion with the medical monitor. For Grade 3 events, treatment with acalabrutinib can be considered after the LFT laboratory values have returned to Grade ≤ 1 or to baseline.

Note: Temporary withholding of study drug for as little as 7 days can cause a transient worsening of disease and/or of constitutional symptoms. Refer to [Section 3.12](#) for more information on assessing disease progression under these circumstances.

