	
Although acalabrutinib has not demonstrated any dose-limiting toxicities (DLTs) to date, the safety of acalabrutinib in combination with pembrolizumab in this patient population needs to be assessed and standard DLT criteria will be applied to Arm 2 of the study. Therefore an interim safety analysis will occur once 6 subjects have been successfully randomized to the combination arm (Arm 2) and have been treated a minimum of 4 weeks. Enrollment will be paused while the interim safety analysis occurs. If a DLT rate of < 33% is observed in Arm 2 (ie, DLT review is cleared), then randomization will continue to evaluate the objective response rates of pembrolizumab monotherapy and the combination of pembrolizumab and acalabrutinib (ie, up to 37 total subjects per arm). If a DLT rate of $\geq 33\%$ is observed in Arm 2, then enrollment (1:1) will continue until an additional 6 subjects are randomized to Arm 2, but with a reduced dose level for acalabrutinib (Level -1). If the DLT review is cleared in those additional 6 subjects in Arm 2 then continued enrollment will occur at Level -1 for the combination arm. If a DLT rate of $\geq 33\%$ is observed in Arm 2 at Level -1, then an additional 6 subjects will be randomized at Level -2 and assessed for DLTs. If the DLT review is cleared, continued enrollment will occur at Level -2 for the combination arm. If the DLT review is not cleared, enrollment will be halted in Arm 2.
 
Acalabrutinib treatment can continue for subjects who are tolerating therapy and not progressing. Pembrolizumab treatment is for 24 months from the date of first dose for subjects who are tolerating therapy and not progressing. Subjects who have confirmed progressive disease on the combination of pembrolizumab and acalabrutinib will discontinue study treatment while those with confirmed progressive disease in the pembrolizumab monotherapy arm will continue on pembrolizumab with the addition of acalabrutinib until a second disease progression or intolerance to therapy. For subjects who cross over to receive combination treatment, acalabrutinib treatment will begin at the next visit at which subjects are scheduled to receive pembrolizumab. The immune-related response criteria (irRECIST; Appendix 8) will be used to determine progression on this study. Pembrolizumab treatment can end for subjects with confirmed complete response (CR) if treatment has been administered for at least 24 weeks and 2 doses of pembrolizumab have been administered after confirmation of CR.
 
Refer to Appendix 4 and Appendix 5 for comprehensive lists of study assessments and their timing. A study schema is provided in Figure 3-1.

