3.5.2 Arm 2 – Combination Treatment

The dose of acalabrutinib is 100 mg BID PO. The doses may be modified for DLTs as summarized in [Table 3-2](#).

Pembrolizumab 200 mg will be administered every 3 weeks by IV infusion for a maximum of 24 months from the date of first dose.

Acalabrutinib and pembrolizumab dosing will begin on the same day (Day 1 of Week 1) except for the first 6 subjects enrolled due to PK sampling. The first 6 subjects enrolled will receive acalabrutinib on Day 1 of Week 1. Then on Day 2 of Week 1 the first pembrolizumab infusion will be administered.

Table 3-2. Dose Reduction for Acalabrutinib

Dose Level	Acalabrutinib	Pembrolizumab
Starting Dose	100 mg BID PO	200 mg Q3W IV
Level -1	100 mg QD PO	200 mg Q3W IV
Level -2	50 mg BID PO	200 mg Q3W IV

Abbreviations: BID = twice per day; IV = intravenous, PO = oral; Q3W = every 3 weeks; QD = once per day

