3.7 ASSESSMENT OF DOSE-LIMITING TOXICITY (DLT)

As outlined in [Section 3.0](#), DLT review will be applied to Arm 2 as the combination of acalabrutinib plus pembrolizumab has not been evaluated before, therefore an interim safety analysis will occur once 6 subjects have been successfully randomized to the combination arm (Arm 2) and have been treated a minimum of 4 weeks. Enrollment will be paused while the interim safety analysis occurs.

A DLT will be defined as the occurrence of any of the following study-drug-related AEs (note: AEs clearly related to disease progression or the subject's current medical history and associated comorbidities will not be considered DLTs):

1. Grade 4 vomiting or diarrhea
2. Grade 3 nausea, vomiting, or diarrhea lasting for > 72 hours
3. Other Grade ≥ 3 toxicities (Note: Transient Grade 3/4 laboratory abnormalities that are not clinically significant will not be considered DLTs)
4. Dosing delay due to toxicity for > 21 consecutive days.

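### Section 3.8 caps acalabrutinib re-escalation at a fixed 100 mg BID, so a subject reduced for toxicity could return to a dose level that has failed the Arm 2 DLT review

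*Protocol*

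**What the plan says.** Table 3-2 (Section 3.5.2) gives three acalabrutinib levels: the starting dose of 100 mg BID, Level -1 at 100 mg QD and Level -2 at 50 mg BID.

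Section 3.7 and the Synopsis (Study Design) place a DLT review after 6 Arm 2 subjects have been treated for at least 4 weeks. If the observed DLT rate is 33% or more, the next 6 Arm 2 subjects are enrolled at Level -1. If that level fails as well, "then an additional 6 subjects will be randomized at Level -2 and assessed for DLTs". Section 3.0 also ties the acalabrutinib dose of subjects crossing over from Arm 1 to this review.

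Section 3.8 deals with individual subjects. When acalabrutinib has been cut for apparent treatment-related toxicity and the lower dose is tolerated for at least 4 weeks, "the dose may be increased to the next higher dose level, at the discretion of the investigator". The one dose limit on that step is that "the maximum dose of acalabrutinib is 100 mg BID for this protocol". On hepatitis the section is stricter: "For Grade 4 events, acalabrutinib may be restarted only after discussion with the medical monitor".

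**The concern.** The DLT review exists to stop the trial giving a dose that too many subjects cannot tolerate. New Arm 2 subjects and crossover subjects both take their dose from its result. Re-escalation does not, because its ceiling is a constant equal to the starting dose. After a failed review, a subject already reduced from the failed dose, possibly because of one of the DLTs that failed it, could be raised to it again without breaching the protocol. Section 3.10.1 warns that transaminase elevations may be more frequent and more severe on the combination, so a failed level cannot be dismissed as a remote possibility.

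**Working it through.** **Inputs.** Cohort of 6 per reviewed level (Section 3.7, Synopsis). Failure at a DLT rate of 33% or more (Synopsis). Dose levels from Table 3-2. Arm 2 maximum of 37 (Synopsis), which agrees with Section 5.1: 6 + 31 = 37. The true DLT rate is not given; 10%, 20% and 30% are assumed here.

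**1. The plan's thresholds.** 1/6 = 16.7% is below 33% and clears; it also meets the 17% MTD limit in Section 5.1. 2/6 = 33.3% fails. So a level fails at 2 or more DLTs in 6, and the two stated thresholds agree.

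**2. Daily dose at each level.** Starting dose 2 × 100 = 200 mg. Level -1: 1 × 100 = 100 mg. Level -2: 2 × 50 = 100 mg. A return from Level -1 to the starting dose doubles the daily dose. A return from Level -2 to Level -1 leaves it unchanged.

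**3. Which doses follow the review.**

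| Subjects | Dose after a failed review | Tied to the review? |
|---|---|---|
| New Arm 2 subjects | Next level down (Synopsis) | Yes |
| Crossover subjects | Set by the review (Section 3.0) | Yes |
| Reduced subjects going back up | One level up, to at most 100 mg BID (Section 3.8) | No |

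**4. Chance that the starting dose fails.** With X ~ Bin(6, p), P(X ≥ 2) = 1 − (1 − p)^6 − 6p(1 − p)^5. The mean number of DLT subjects counted only when the level fails is 6p − P(X = 1); dividing by P(X ≥ 2) gives the mean given failure.

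| Assumed p | P(X ≥ 2) | Mean over all outcomes | Mean given failure |
|---|---|---|---|
| 10% | 1 − 0.5314 − 0.3543 = 0.114 | 0.60 − 0.354 = 0.25 | 2.2 |
| 20% | 1 − 0.2621 − 0.3932 = 0.345 | 1.20 − 0.393 = 0.81 | 2.3 |
| 30% | 1 − 0.1176 − 0.3025 = 0.580 | 1.80 − 0.303 = 1.50 | 2.6 |

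**5. Both the starting dose and Level -1 fail.** With the same rate at both levels: 0.1143² = 1%, 0.3446² = 12%, 0.5798² = 34%. These are too high if the lower dose is safer.

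**6. Reach.** At most about 6 subjects per failed level, or 6/37 = 16% of Arm 2 at its maximum, and only if all six had been reduced. For the starting dose these are first-cohort subjects. For Level -1 they are any subjects reduced from it to Level -2, including second-cohort subjects who began at Level -1.

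**The case against.** Several points on the other side stand.

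- **Many DLTs end the combination.** Table 3-3 and Section 3.8.2 stop pembrolizumab permanently for Grade 3–4 pneumonitis, nephritis and infusion reactions, for Grade 3–4 liver test elevations (with an exception for some subjects with liver metastases), and for most other Grade 4 toxicities. Such a subject could return only to acalabrutinib alone, and Section 3.2 reports no DLT with acalabrutinib in the CLL study at up to 200 mg BID. The DLT counts above therefore overstate re-exposure to the failed combination. They are a rough proxy in the other direction too, since some subjects would be reduced for events that are not DLTs.
- **The step is cautious.** It is optional, one level at a time, and needs 4 weeks' tolerance. A cohort result of 2 in 6 does not show that a given individual cannot tolerate the dose, and Section 3.8 singles out events later judged unrelated.
- **There is oversight.** Section 3.14 provides continuous internal review of AEs and quarterly calls covering AEs that led to dose reductions. But it sets no dose limit and no approval step before re-escalation. The Bayesian toxicity rule in Section 5.5 begins at 10 subjects and governs enrollment, not individual dosing.
- **The branch may not have arisen.** Appendix 5 lists crossover acalabrutinib at 100 mg BID, and Section 3.0 ties that dose to the review. This suggests, without establishing, that the starting dose cleared.

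A reader might infer more than the text supports. It does not let subjects whose assigned dose is Level -1 climb to 100 mg BID, because re-escalation in Section 3.8 follows a reduction. It does not show that any level failed. And a return from Level -2 to Level -1 is not an increase in daily dose.

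**Conclusion.** The gap is real but small and conditional. Followed as written, Section 3.8 permits a return to a dose level that the DLT review has failed, and no other section prevents it. The consequential case is the starting dose: a rise from 100 to 200 mg/day for a few first-cohort subjects, in a branch with probability 11% to 58% over assumed DLT rates of 10% to 30%. The Level -1 case alters the dosing schedule only. Fewer than 6 subjects per failed level are likely to be affected, because many DLTs end pembrolizumab and some subjects would stop treatment altogether. The point rests on the wording of Section 3.8. The probabilities rest on the assumed rates and show only that a failed review is plausible. Sample size and efficacy analyses are untouched.

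**What to change.** Replace the last sentence of the first paragraph of Section 3.8 with:

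> *However, acalabrutinib may not be re-escalated to a dose level that has failed the Arm 2 DLT review, and the maximum dose is 100 mg BID for this protocol.*

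Barring failed levels is better than limiting re-escalation to the highest cleared level, which has no meaning until some level has cleared and would block re-escalation before the review. The sentence changes nothing if the starting dose cleared.

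The cost is one sentence, with no effect on sample size, visits or analysis. The downside is that a few subjects from a failed cohort, including any whose AE later proves unrelated to treatment, lose the option of going back to that dose. The sentence does not settle what happens to first-cohort subjects who were never reduced and are still taking a failed dose. The Synopsis gives no rule for them, and the sponsor could state one in the same amendment.

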3.8.1 Dose Modifications for Pembrolizumab

AEs (nonserious and serious) associated with pembrolizumab exposure may represent an immunologic etiology. These AEs may occur shortly after the first dose or several months after the last dose of treatment. Pembrolizumab must be withheld for drug-related toxicities and severe or life-threatening AEs as per [Table 3-3](#) below. See [Section 3.8.2](#) for supportive care guidelines, including use of corticosteroids.

Table 3-3. Dose Modification Guidelines for Drug-Related Adverse Events

Toxicity	Hold Treatment For Grade	Timing for Restarting Treatment	Treatment Discontinuation
Diarrhea/Colitis	2-3	Toxicity resolves to Grade 0-1.	Toxicity does not resolve within 12 weeks of last dose or inability to reduce corticosteroid to 10 mg or less of prednisone or equivalent per day within 12 weeks.
	4	Permanently discontinue	Permanently discontinue
AST, ALT, or Increased Bilirubin	2	Toxicity resolves to Grade 0-1	Toxicity does not resolve within 12 weeks of last dose.
	3-4	Permanently discontinue (see exception below) ^a	Permanently discontinue
Type 1 diabetes mellitus (if new onset) or Hyperglycemia	T1DM or 3-4	Hold pembrolizumab for new onset Type 1 diabetes mellitus or Grade 3-4 hyperglycemia associated with evidence of beta cell failure.	Resume pembrolizumab when patients are clinically and metabolically stable.
Hypophysitis	2-4	Toxicity resolves to Grade 0-1. Therapy with pembrolizumab can be continued while endocrine replacement therapy is instituted	Toxicity does not resolve within 12 weeks of last dose or inability to reduce corticosteroid to 10 mg or less of prednisone or equivalent per day within 12 weeks.
Hyperthyroidism	3	Toxicity resolves to Grade 0-1	Toxicity does not resolve within 12 weeks of last dose or inability to reduce corticosteroid to 10 mg or less of prednisone or equivalent per day within 12 weeks.
	4	Permanently discontinue	Permanently discontinue
Hypothyroidism		Therapy with pembrolizumab can be continued while thyroid replacement therapy is instituted	Therapy with pembrolizumab can be continued while thyroid replacement therapy is instituted.
Infusion Reaction	2 ^b	Toxicity resolves to Grade 0-1	Permanently discontinue if toxicity develops despite adequate premedication.
	3-4	Permanently discontinue	Permanently discontinue
Pneumonitis	2	Toxicity resolves to Grade 0-1	Toxicity does not resolve within 12 weeks of last dose or inability to reduce corticosteroid to 10 mg or less of prednisone or equivalent per day within 12 weeks.

Toxicity	Hold Treatment For Grade	Timing for Restarting Treatment	Treatment Discontinuation
	3-4	Permanently discontinue	Permanently discontinue
Renal Failure or Nephritis	2	Toxicity resolves to Grade 0-1	Toxicity does not resolve within 12 weeks of last dose or inability to reduce corticosteroid to 10 mg or less of prednisone or equivalent per day within 12 weeks.
	3-4	Permanently discontinue	Permanently discontinue
All Other Drug-Related Toxicity ^c	3 or Severe	Toxicity resolves to Grade 0-1	Toxicity does not resolve within 12 weeks of last dose or inability to reduce corticosteroid to 10 mg or less of prednisone or equivalent per day within 12 weeks.
	4	Permanently discontinue	Permanently discontinue

Note: Permanently discontinue for any severe or Grade 3 (Grade 2 for pneumonitis) drug-related AE that recurs or any life-threatening event.

a. For patients with liver metastasis who begin treatment with Grade 2 AST or ALT, if AST or ALT increases by greater than or equal to 50% relative to baseline and lasts for at least 1 week then patients should be discontinued.

b. If symptoms resolve within one hour of stopping drug infusion, the infusion may be restarted at 50% of the original infusion rate (e.g., from 100 mL/hr to 50 mL/hr). Otherwise dosing will be held until symptoms resolve and the subject should be premedicated for the next scheduled dose; Refer to [Table 3-4](#) for further management details.

c. Patients with intolerable or persistent Grade 2 drug-related AE may hold study medication at physician discretion. Permanently discontinue study drug for persistent Grade 2 adverse reactions for which treatment with study drug has been held, that do not recover to Grade 0-1 within 12 weeks of the last dose.

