 - For **Grade 2** events, treatment with pembrolizumab should be withheld. Administer corticosteroids (initial dose of 0.5 to 1 mg/kg/day prednisone or equivalent) ([Appendix 6](#)). When LFT laboratory values resolve to baseline or return to Grade ≤ 1 , then taper the corticosteroids over no fewer than 4 weeks while continuing to monitor LFTs at least weekly. Further treatment with pembrolizumab can be considered after the LFT laboratory values have returned to Grade ≤ 1 or to baseline either during the steroid taper or after stopping corticosteroids.
 - For **Grade 3-4** events, permanently discontinue pembrolizumab. Treat with corticosteroids initial dose 1 to 2 mg/kg/day prednisone or equivalent) ([Appendix 6](#)) until LFT laboratory values resolve to baseline or return to Grade ≤ 1 , and then taper the corticosteroids over no fewer than 4 weeks while continuing to monitor LFTs at least weekly.
- **Renal Failure or Nephritis:**
 - For **Grade 2** events, treat with corticosteroids.
 - For **Grade 3-4** events, treat with systemic corticosteroids.
 - When symptoms improve to Grade 1 or less, steroid taper should be started and continued over no less than 4 weeks.
- **Management of Infusion Reactions:**
 - Signs and symptoms usually develop during or shortly after drug infusion and generally resolve completely within 24 hours of completion of infusion.
 -

- [Table 3-4](#) shows treatment guidelines for subjects who experience an infusion reaction associated with administration of pembrolizumab.

Table 3-4. Infusion Reaction Treatment Guidelines

NCI CTCAE Grade	Treatment	Premedication at subsequent dosing
Grade 1 Mild reaction; infusion interruption not indicated; intervention not indicated	Increase monitoring of vital signs as medically indicated until the subject is deemed medically stable in the opinion of the investigator.	None

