3.10 PRECAUTIONS

3.10.1 Transaminase Elevations for Acalabrutinib in Combination with Pembrolizumab

Serum transaminase elevations (including elevations of AST and/or ALT) may be increased in severity and frequency in subjects exposed to the combination of acalabrutinib and pembrolizumab, as compared with subjects exposed to pembrolizumab monotherapy and subjects exposed to acalabrutinib monotherapy. Routine monitoring for serum transaminase elevations must follow the Schedule of Assessments (serum chemistry lab assessments). Dosing delays and modifications for subjects with serum transaminase elevations must follow guidance provided in [Section 3.8](#).

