3.12 WITHDRAWAL OF SUBJECTS FROM STUDY TREATMENT

Any subject has the right to withdraw from the study at any time.

- Study treatment should be discontinued in the event of a toxicity lasting > 28 consecutive days, unless reviewed and approved by the medical monitor.
- Any subject who has confirmed objective evidence of cancer progression while receiving acalabrutinib and pembrolizumab should discontinue study treatment.
Note: Study subjects receiving immunotherapies can experience transient immunotherapy-related increases in lesion size (“pseudoprogression”) preceding tumor regression ([Hodi 2010](#)). If there is uncertainty regarding whether there is true cancer progression, the subject may continue study treatment and remain under close observation (eg, evaluated at 4-week intervals) pending confirmation of progression ([Section 3.11](#)). In particular, transient worsening of disease early in therapy or during temporary interruption of study therapy (eg, for drug-related toxicity, surgery, or intercurrent illness) may not indicate cancer progression. In such circumstances, and if medically appropriate, subjects may resume therapy and relevant clinical, laboratory, and/or radiographic assessment can be attempted to document whether tumor control can be maintained or whether cancer progression has occurred.
- Any subject whose medical condition substantially changes after entering the study should be carefully evaluated by the investigator in consultation with the

medical monitor. Such subjects should be withdrawn from study treatment if continuing would place them at risk.

- Any subject who becomes pregnant should be removed from study treatment.
- Any subject who becomes significantly noncompliant with study drug administration, study procedures, or study requirements should be withdrawn from study treatment in circumstances that increase risk or substantially compromise the interpretation of study results.
- The investigator, in consultation with the medical monitor, may withdraw any subject from study treatment, if, in the investigator's opinion, it is not in the subject's best interest to continue.

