2.3 Dose Modifications

Withhold KEYTRUDA for any of the following:

- Grade 2 pneumonitis [see *Warnings and Precautions* (5.1)]
- Grade 2 or 3 colitis [see *Warnings and Precautions* (5.2)]
- Grade 3 or 4 endocrinopathies [see *Warnings and Precautions* (5.4)]
- Grade 2 nephritis [see *Warnings and Precautions* (5.5)]
- Aspartate aminotransferase (AST) or alanine aminotransferase (ALT) greater than 3 and up to 5 times upper limit of normal (ULN) or total bilirubin greater than 1.5 and up to 3 times ULN
- Any other severe or Grade 3 treatment-related adverse reaction [see *Warnings and Precautions* (5.6)]

Resume KEYTRUDA in patients whose adverse reactions recover to Grade 0-1.

Permanently discontinue KEYTRUDA for any of the following:

- Any life-threatening adverse reaction (excluding endocrinopathies controlled with hormone replacement therapy)
- Grade 3 or 4 pneumonitis or recurrent pneumonitis of Grade 2 severity [see *Warnings and Precautions* (5.1)]
- Grade 3 or 4 nephritis [see *Warnings and Precautions* (5.5)]
- AST or ALT greater than 5 times ULN or total bilirubin greater than 3 times ULN
 - For patients with liver metastasis who begin treatment with Grade 2 AST or ALT, if AST or ALT increases by greater than or equal to 50% relative to baseline and lasts for at least 1 week
- Grade 3 or 4 infusion-related reactions [see *Warnings and Precautions* (5.7)]

- Inability to reduce corticosteroid dose to 10 mg or less of prednisone or equivalent per day within 12 weeks
- Persistent Grade 2 or 3 adverse reactions (excluding endocrinopathies controlled with hormone replacement therapy) that do not recover to Grade 0-1 within 12 weeks after last dose of KEYTRUDA
- Any severe or Grade 3 treatment-related adverse reaction that recurs [see *Warnings and Precautions (5.6)*]

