5.3 Immune-Mediated Hepatitis

Immune-mediated hepatitis occurred in patients receiving KEYTRUDA. Monitor patients for changes in liver function. Administer corticosteroids (initial dose of 0.5 to 1 mg/kg/day [for Grade 2 hepatitis] and 1 to 2 mg/kg/day [for Grade 3 or greater hepatitis] prednisone or equivalent followed by a taper) and, based on severity of liver enzyme elevations, withhold or discontinue KEYTRUDA [*see Dosage and Administration (2.3) and Adverse Reactions (6.1)*].

Melanoma

Hepatitis occurred in 16 (1.0%) of 1567 patients receiving KEYTRUDA in Trials 1, 2, and 6, including Grade 2 (0.1%), Grade 3 (0.7%), and Grade 4 (0.1%) hepatitis. The time to onset was 26 days (range: 8 days to 21.4 months). The median duration was 1.2 months (range: 8 days to 4.7 months). Eleven (69%) of the 16 patients received corticosteroids, with 10 of the 11 receiving high-dose systemic corticosteroids for a median duration of 5 days (range: 1 to 14 days) followed by a corticosteroid taper. Hepatitis led to discontinuation of KEYTRUDA in 6 (0.4%) patients. Hepatitis resolved in 14 (88%) of the 16 patients.

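### Table 3-3: of the five rows that hold pembrolizumab at Grade 2 and are treated with corticosteroids, only AST/ALT/bilirubin lacks the 12-week prednisone stop

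*Protocol*

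**What the plan says.** Table 3-3 (Protocol Section 3.8.1) holds pembrolizumab for Grade 2 AST, ALT or bilirubin elevation and allows a restart once the toxicity is back to Grade 0-1. Its discontinuation cell has one condition: "Toxicity does not resolve within 12 weeks of last dose". The Grade 2 rows for diarrhea/colitis, hypophysitis, pneumonitis and renal failure/nephritis have the same condition and then a second: "or inability to reduce corticosteroid to 10 mg or less of prednisone or equivalent per day within 12 weeks". The Grade 3 hyperthyroidism row and the Grade 3 All Other row carry the second condition too.

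Section 3.8.2 treats Grade 2 hepatic events with steroids: "Administer corticosteroids (initial dose of 0.5 to 1 mg/kg/day prednisone or equivalent". A taper of at least 4 weeks follows, with liver tests at least weekly. Further pembrolizumab can be considered at Grade 1 or less (or baseline), during the taper or after it.

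The package insert in Appendix 6 (its section 2.3) lists as a general reason for permanent discontinuation: "Inability to reduce corticosteroid dose to 10 mg or less of prednisone or equivalent per day within 12 weeks". It makes no exception for liver.

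Section 3.10.1 warns that transaminase elevations may be more frequent and more severe on the combination. It then says: "Dosing delays and modifications for subjects with serum transaminase elevations must follow guidance provided in" Section 3.8.

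**The concern.** The table treats failure to resolve and failure to come off steroids as two separate stops, joined by an or. In the liver row, the first therefore cannot be read as including the second. Liver tests can sit at Grade 0-1 because prednisone is holding them there. In the four comparable rows, such a subject stops pembrolizumab at week 12. In the liver row nothing stops it, and no reason for the difference is given.

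What is at stake is subject safety, not inference. Transaminase elevation on the combination is the stated reason for Amendment 4, so this is an awkward row in which to lack a safeguard that the neighbouring rows have.

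**Working it through.** The protocol states no figure to reproduce. The check compares the rows and then asks how many subjects could be affected.

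**1. Rows that hold at Grade 2 and get corticosteroids at Grade 2 under Section 3.8.2**

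| Row | Grade held | Stop: unresolved at 12 weeks | Stop: prednisone not at 10 mg/day or less within 12 weeks |
|---|---|---|---|
| Diarrhea/colitis | 2-3 | yes | yes |
| Hypophysitis | 2-4 | yes | yes |
| Pneumonitis | 2 | yes | yes |
| Renal failure/nephritis | 2 | yes | yes |
| AST/ALT/bilirubin | 2 | yes | **no** |

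Four of five carry the steroid stop, and liver is the exception. The remaining rows without it are not comparators: type 1 diabetes/hyperglycemia is managed with insulin, hypothyroidism is not held, and Grade 2 infusion reactions are treated symptomatically.

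**2. Does other text supply the rule?**

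- Footnote a to Table 3-3 concerns liver metastasis with Grade 2 AST or ALT at the start of treatment.
- Footnote c belongs to the All Other row and has no steroid condition.
- The table's closing note on recurrence applies to Grade 3 or severe events (Grade 2 only for pneumonitis) and to life-threatening events.
- Section 3.9.2 allows steroids at any required dosage for immune-mediated reactions, so it sets no ceiling.
- Section 3.12 stops treatment for a toxicity lasting more than "28 consecutive days, unless reviewed and approved by the medical monitor". That depends on the toxicity persisting and can be waived. It does not clearly catch a subject already at Grade 0-1 on steroids.

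**3. When would a subject be above 10 mg/day at week 12?**

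Assume a body weight of 60 to 90 kg, a linear 28-day taper to zero, and both 12-week clocks starting at the last pembrolizumab dose.

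- Starting dose: 0.5 × 60 = 30 mg/day up to 1 × 90 = 90 mg/day.
- Days of taper to reach 10 mg: 28 × (1 − 10/30) = 18.7, up to 28 × (1 − 10/90) = 24.9. That is about day 19 to day 25.
- Week 12 is day 84. A single such taper is still above 10 mg/day only if it began after about day 84 − 19 = 65 (30 mg start) or day 84 − 25 = 59 (90 mg start).

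The gap therefore needs late resolution, a longer taper or repeated tapers. Section 3.8.2 itself warns that several taper courses may be needed, so the case is foreseeable but not routine.

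**4. How many subjects could enter the row?**

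The row is triggered by a Grade 2 laboratory elevation. The nearest figure is in Appendix 6, Table 6 (NSCLC, pembrolizumab alone, n = 550): increased AST in 20% at all grades and 1% at Grades 3-4.

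- Grades 1 and 2 together: 20% − 1% = 19%.
- Grade 2 alone is not split out, so it lies between 0 and about 19%.
- With up to 37 subjects per arm: 0 to 0.19 × 37 = 7.03, or about 7.

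This is a range for AST only. That table gives no ALT or bilirubin figure, it is not limited to drug-related elevations, and no rate is stated for the combination. The share of these subjects still above 10 mg/day at week 12 is given nowhere.

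**The case against.** The best case against is that liver is already the most closely specified organ. Its entry in Section 3.8.2 has mg/kg steroid doses, at least weekly testing through the taper, and a restart rule that mentions steroids directly. A different stopping rule could be deliberate. Restart is at the investigator's discretion, a flare to Grade 2 triggers the hold again, and Grade 3-4 is a permanent stop. Sections 1.4 and 1.8 also point readers to the label for fuller information on pembrolizumab. All of this stands as mitigation and keeps the point small. It does not supply the missing stop: Table 3-3 is the operative instruction, and no text presents liver as an intended exception.

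A reader might infer more than the documents support:

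- *That liver is alone among all Grade 2 rules.* It is not. Footnote c, on other Grade 2 reactions "that do not recover to Grade 0-1 within 12 weeks of the last dose", has no steroid condition either. The contrast is with the four named rows.
- *That six of seven steroid-managed rows carry the clause.* That count includes All Other, for which Section 3.8.2 has no steroid entry.
- *That restarting while on steroids is itself a liver defect.* The comparator rows also allow a restart at Grade 0-1 with no dose ceiling. Only the 12-week stop differs.
- *That the label's hepatitis rate sizes the problem* ("including Grade 2 (0.1%), Grade 3 (0.7%), and Grade 4 (0.1%) hepatitis"). That is immune-mediated hepatitis in melanoma, a different event from the laboratory elevation that triggers this row.
- *That the citation of Appendix 6 in the hepatic paragraph brings in the label's stop.* It is attached to the steroid dose only.

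**Conclusion.** The omission is real. Among the five rows that hold at Grade 2 and are treated with corticosteroids, only AST/ALT/bilirubin lacks the 12-week prednisone stop, and the appended label has no such exception. A subject at Grade 0-1 but above 10 mg/day at week 12 may resume or stay on pembrolizumab under the current text.

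The number affected cannot be derived. On monotherapy, between 0 and about 7 of 37 subjects could have a Grade 2 AST elevation. Those who meet the gap are an unstated, probably small, fraction of them. That judgement rests on the taper arithmetic and its assumed weights, and the rate on the combination is unknown. Sample size, power and the primary response analysis are untouched. This is a minor harmonising correction.

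**What to change.** In Table 3-3, extend the Grade 2 AST/ALT/bilirubin discontinuation cell with the clause already used in the other rows: "or inability to reduce corticosteroid to 10 mg or less of prednisone or equivalent per day within 12 weeks". In the Grade 2 hepatic paragraph of Section 3.8.2, add a cross-reference to the Table 3-3 discontinuation rule. Do not add a separate steroid ceiling for restart, since the comparator rows have none.

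The cost is one clause and one cross-reference, which can go into the next amendment. No new procedure or data collection is needed. The downside is that an occasional subject stops pembrolizumab earlier than under the current text, as the comparator rows and the label already require.
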